10.2.3 Target Days and Analysis Visit Windows

Analysis visit windows are summarized in Table 10.2-1 for efficacy data, and on Table 10.2-2 and Table 10.2-3 for pharmacokinetic data.

When there are multiple observations within a visit window, the value closest to the target day will be analyzed, with the earliest date/time used in the event of ties.

For visit based efficacy endpoints, visit windowing will apply whether patient is on- or off-treatment.

Visit / Day	Analysis visit	Target day	MSSS-88	T25FW SF-36
Visit 2 / Day 1*	Baseline	1 (predose)	-28 to 1 (predose)	-28 to 1 (predose)
Visit 3 / Day 15	Week 2	15	NA	NA
Visit 4 / Day 29	Week 4	29	NA	NA
Visit 5 / Day 57	Week 8	57	2 to 71	NA
Visit 6 / Day 85**	Week 12	85	72 to 92	2 to 92
Visit 7 / Day 99 ***	Week 14	99	NA	NA

Table 10.2-1 Longitudinal Efficacy and QoL Assessment – Target Day and Analysis Visit Window

MSSS-88 = Multiple sclerosis spasticity scale; T25FW=Timed 25-foot walk; SF-36=36-items Short form health Survey; NA = Not applicable.

* Day 1 is based on the date of randomization.

** Will also be completed for those patients who permanently withdraw from the study.

*** Follow-up visit is expected to be completed between 10 and 14 days following early study withdrawal.

^{***} Follow-up visit is not required to be completed for any patient who discontinue IMP but continue offtreatment provided that Visit 6 is completed.

Table 10.2-2 Semi-intensive PK Draw Assessment – Target Day and Time and Visit/Time Window

		Target C	Day window	Target time			
visit / Day	Analysis visit	day		Н0	H2-H3	H4-H6	H6-H8
Visit 2 / Day 1*	Baseline	1	-28 to 1	predose			
Visit 3 / Day 15 or Visit 4 / Day 29 or Visit 5 / Day 57	Week 2 to Week 8	15 or 29 or 57	2 to 71	predose	H0 + 2 hours to H0 + 3 hours	H2-H3 + 2 hours to H2-H3 + 4.5 hours	H4-H6 + 2hours H5_H6 + 4.5 hours

H=Hour; IMP=Investigational medicinal product

* Day 1 is based on the date of first IMP spray administration

Table 10.2-3 Sparse PK Draw Assessment – Target Day and Analysis Visit Window

Visit / Day	Analysis visit	Target day	Sparse PK sampling
Visit 2 / Day 1*	Baseline	1 (predose)	-28 to 1 (predose)
Visit 3 / Day 15**	Week 2	15	2 to 22
Visit 4 / Day 29**	Week 4	29	23 to 43
Visit 5 / Day 57**	Week 8	57	44 to 71
Visit 6 / Day 85**	Week 12	85	72 to 92

PK=Pharmacokinetic.

* Day 1 is based on the date of first IMP spray administration

** Sample collected at any time during the visit

10.2.4 Reporting of Longitudinal Safety Assessments

Physical examination, serum urine pregnancy test, dipstick urinalysis, examination of oral mucosa, vital signs, body weight, 12-lead ECG, clinical laboratory blood sampling, C-SSRS, MUS will be summarized using the nominal visit. In case of repeat assessments, the original assessment will be used in summaries, but all assessments will be listed.

For patients that discontinued IMP early but remained on study, assessments taken after IMP End Date will be assigned to the Follow-up visit, as long as they are within 30 days of IMP End Date.

For examination of oral mucosa, vital signs, body weight, 12-lead ECG, clinical laboratory blood sampling and C-SSRS the last on-treatment assessment will also be identified. The last on-treatment assessment is defined as the last scheduled assessment prior to IMP End Date, only assessments after the IMP Start Date will be considered (see Section 10.1 for source of dates).

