# 5.3.4 Investigational Medicinal Product Accountability

The investigator has overall responsibility for the accountability of all used and unused IMP. A drug accountability record for the IMPs must be kept current and must contain the following:

- Trial code
- Packaging reference number, date of receipt, and quantity of IMP received
- Patient's trial unique patient number and/or treatment number
- Date and quantity of IMP dispensed
- The initials of the dispensing/dosing party
- Date and quantity of IMP returned to the investigator
- IMP expiry dates

IMP will be dispensed at Visits 2, 3, 4, and 5. Patients will be asked to return all IMP (used and unused) at each subsequent visit (Visits 3, 4, 5, and 6). The trial site will check the returned IMP against the usage recorded in the electronic diary via electronic Clinical Report Form (eCRF) accountability calculations. Any discrepancies will be discussed with the patient at the time of the visit and documented accordingly within the patient's source documents. Refer to Section 9.2.18.2.1 for the list of triggering drug accountability discrepancies associated with monitoring of drug abuse liability.

The investigator must inform GW promptly of all missing or unaccountable IMP.

A record of returned IMP must be completed and included in the shipment of used and unused IMP to the relevant drug distribution depot. At the end of the trial, a record/statement of reconciliation must be completed and provided to GW.

These inventories must be made available for inspection by an authorized GW representative and local officials or regulatory agency inspectors.

Please refer to the separate pharmacy manual for more detailed information on the IMP.

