# 9.1.4 Visit 6 (Day 85, End of Treatment Visit/Withdrawal Visit)

This visit will occur 84 days after the first dose of IMP or earlier, if the patient withdraws from the trial. A visit window of  $\pm$  7 days from the scheduled visit date is permitted, but it is preferred that the visit is performed on the scheduled visit day, where possible.

Patients who discontinue IMP treatment early will be encouraged to continue (off treatment) in the trial and to complete all remaining trial procedures to Visit 6 (Day 85), where possible.

The following assessments/procedures will be performed:

- Concomitant medications review
- AE review
- Physical and oral mucosa examinations
- Body weight measurement
- Vital signs measurement
- 12-lead ECG
- Clinical laboratory blood sampling (hematology and biochemistry)
- PK blood sampling (see Section 9.2.12.1)
- Dipstick urinalysis
- Serum pregnancy test (if appropriate)
- MSSS-88 assessment
- C-SSRS assessment
- T25FW test

V1, 24Sep15

- Medication Use Survey (MUS [Section 9.2.15.5])
- SF-36 assessment
- IMP collection and compliance review

Patients should be reminded to record their spasm count, 11-point NRS spasm severity score, 11-point NRS spasticity score, and use of antispasticity medications in the electronic diary once daily, around the same time of the day, preferably in the evening before retiring to sleep.

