Following randomization (Visit 2 [Day 1]), patients will attend the trial site on Visit 3 (Day 15), Visit 4 (Day 29), and Visit 5 (Day 57). The End of Treatment Visit (Visit 6) will occur on Day 85 (± 7 days). Patients who discontinue IMP early will be encouraged to continue (off treatment) in the trial and to complete all remaining trial procedures up to the End of Treatment/Early Withdrawal Visit (Visit 6 [Day 85]), where possible.

A Safety Follow-up Visit (Visit 7 [Day 99]) will take place 14 (\pm 4) days after the End of Treatment Visit or Early Withdrawal Visit for all patients except those who discontinue IMP but complete scheduled trial visits.

Patients who complete the trial will participate for a total of approximately 18 weeks (127 days), including the 28-day baseline period. Patients will have a maximum duration of 85 (\pm 7) days on IMP.

Approximately 65 sites (USA and Europe) are expected to participate in this trial. Additional trial sites may be used in order to supplement recruitment. Although no minimal number of patients are required to come from USA sites, the IRT was designed to make all efforts to have at least 100 US patients.

The study overview is specified in Figure 8.1-1.

The schedule of study events is specified in clinical protocol appendix 1.

Figure 8.1-1 Trial Design and Treatment Schematic

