10.0 Conventions and Derivations

10.1 Source of Key Dates

- The IMP Start Date will be assumed to be the first date of IMP dispense, which will be obtained from the IRT data. If there is documented confirmation that patient did not take IMP eg where this is reported as a protocol deviation, the IMP Start Date will be set to missing.
- The IMP End Date will be taken from eCRF "End of treatment" form.
- The Last Day in Study will be taken from "Study Completion/Discontinuation Date" on the "End of study" form for patients that completed or discontinued early for any reason other than Lost to Follow-up. For patients Lost to Follow-up, the Last Day in Study will be their last contact date.

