10.4.2 Clinic Based Endpoint

For visit based endpoints, the baseline is defined as the last assessment prior to IMP Start Date or prior to randomization if IMP Start Date is after the date of randomization.

However, for C-SSRS, only the assessment carried out at Visit 2 should be used as the baseline assessment.

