10.8 Patient Disposition and Treatment Duration

The time in study expressed in days is defined as:

```
(Last Day in Study – date of randomization) + 1
```

See Section 10.1 for source of dates.

The duration of IMP exposure expressed in days will be derived as:

(IMP End Date – IMP Start Date) + 1

See Section 10.1 for source of dates.

Duration of IMP will also be categorized as follows:

- 1 to 14 days
- 15 to 28 days
- 29 to 56 days
- 57 to 84 days
- 85 to 91 days
- > 91 days

The treatment arm total duration of IMP exposure expressed in patient-years will be derived as follows:

$$\frac{\sum_{i=1}^{i=n} Di}{365.25}$$

With n being the number of patients within the treatment arm and SAF and i=1,2, 3,...,n, and, with Di being the duration of IMP exposure (in days) for patient i.

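### As written, SAP 10.2.4 leaves a treatment completer's Visit 6 out of the last on-treatment safety rows and conflicts with the SAP's own safety on-treatment period (minor)

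*SAP*

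**What the plan says.** SAP 10.2.4 sets one rule for oral mucosa, vital signs, body weight, ECG, laboratory blood tests and C-SSRS: "The last on-treatment assessment is defined as the last scheduled assessment prior to IMP End Date". Only assessments after IMP Start Date count. For patients who stop IMP early but stay on study, the same section says "assessments taken after IMP End Date will be assigned to the Follow-up visit", provided they fall within 30 days of that date.

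The end date has one source, SAP 10.1: "The IMP End Date will be taken from eCRF", namely the End of treatment form. SAP 8.1 gives a ceiling: "Patients will have a maximum duration of 85" (± 7) days. SAP 10.8 fixes the count: "The duration of IMP exposure expressed in days will be derived as" end date minus start date, plus one. Protocol 9.1.4 says of Visit 6: "This visit will occur 84 days after the first dose of IMP", with a window of ± 7 days. Under Protocol 5.3.4 the last dispensing is at Visit 5, and used and unused IMP comes back at Visit 6.

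SAP 12.8 runs the safety analyses over the on-treatment period of SAP 10.2.2. For safety, that period ends 30 days after IMP End Date.

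**The concern.** An assessment held on IMP End Date is neither prior to it nor after it, and one held the next day is not prior to it either. A completer's Visit 6 is in one of these two positions. A programmer who codes the sentence as a strict date comparison will skip Visit 6 and fall back to the previous scheduled assessment.

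The row labelled last on-treatment would then show mid-treatment values, where a reader expects the end-of-treatment state. For laboratory tests, ECG and weight, Visits 4 and 6 are the only scheduled post-dose collections, so completers' entries would simply repeat Visit 4.

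The SAP would also classify the same Visit 6 value in two ways. It is on-treatment for minimum, maximum and worst values, because the 10.2.2 period covers it, but it is not eligible as the last on-treatment value.

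The other sections do not settle this. SAP 12.8.4 and 12.8.5.1 to 12.8.5.3 refer back to 10.2.4 or use its term. SAP 12.8.3 sends the reader to Section 10.24, which does not contain the definition.

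**Working it through.** **Inputs**
- First dose on Day 1 (Protocol 9.1.2).
- Visit 4 on Day 29 ± 3, so Days 26 to 32; Visit 5 on Day 57 ± 7, so Days 50 to 64 (Protocol 9.1.3).
- Visit 6 on Day 85 ± 7, so Days 78 to 92 (Protocol 9.1.4).
- Visit 7 at 14 ± 4 days after Visit 6 (Protocol 9.1.5).
- Post-dose laboratory tests, ECG and weight at Visits 4 and 6. Oral mucosa and C-SSRS at Visits 3 to 6. Vital signs at Visits 3 to 7 (Protocol Appendix 1).

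**Step 1: reproduce the plan's own figure.** Exposure = End − Start + 1. With End = Day 85: 85 − 1 + 1 = 85 days. The ends of the Visit 6 window give 78 and 92 days, which is 85 ± 7. The stated ceiling is therefore reached when the last dose falls on the Visit 6 day. IMP is handed back at that visit, so dosing under the protocol does not run beyond it.

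**Step 2: apply the rule to a Visit 6 on Day 85.**
- Last dose on the Visit 6 day (End = 85): 85 < 85 is false.
- Last dose the evening before (End = 84): 85 < 84 is false.

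Visit 6 fails in both cases. Moving Visit 6 within its window moves both dates together and changes nothing.

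**Step 3: what is selected instead**

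| Data | Selected | Nominal gap to Visit 6 | Range over visit windows |
|---|---|---|---|
| Laboratory tests, ECG, weight/BMI | Visit 4, Day 29 | 85 − 29 = 56 days | 78 − 32 = 46 to 92 − 26 = 66 |
| Vital signs, oral mucosa, C-SSRS | Visit 5, Day 57 | 85 − 57 = 28 days | 78 − 64 = 14 to 92 − 50 = 42 |

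As a share of an 85-day exposure, 56/85 = 66% and 28/85 = 33% would follow the value shown.

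**Step 4: compare with the 10.2.2 safety period.** With End = 85 the period reaches Day 85 + 30 = 115; with End = 84 it reaches Day 114. Visit 6 on Day 85 lies inside both. So does Visit 7 on Day 99, since it comes 10 to 18 days after Visit 6.

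**Step 5: test the simple repairs.**
- On or before IMP End Date, alone: 85 ≤ 85 is true, but 85 ≤ 84 is false. It still loses Visit 6 after an evening-before last dose.
- Within 30 days of IMP End Date, alone: Visit 6 qualifies, but so does Visit 7, which would become the last on-treatment value for vital signs.

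Neither repair is enough alone, so the rule has to name the visits.

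**The case against.** The strongest reply is that nobody would program the sentence literally. SAP 10.4.2 uses the same phrase for visit-based endpoints: "the baseline is defined as the last assessment prior to IMP Start Date". IMP Start Date is the first dispensing date, which is the Visit 2 day, and the predose Visit 2 assessment is plainly the intended baseline. A strict comparison there would discard the Visit 2 laboratory, ECG and vital-sign baselines. This argument stands as evidence of intent: Visit 6 was meant to count. It does not supply a rule, and Step 5 shows that reasonable repairs give different rows.

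A second reply is that 85 days is a ceiling, not an expected last-dose date, and that the form supplying the date has not been seen. Both are true. The conclusion needs only that the recorded end date is not later than Visit 6, which the return of all IMP at that visit supports.

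A third reply is that the effect is small and would show itself, because completers' last on-treatment laboratory values would match Visit 4 beside a populated Visit 6 row. That also stands, and it is why the point is rated minor.

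A reader might infer that Visit 6 safety data drop out of the report. They do not. SAP 10.2.4 summarizes these assessments by nominal visit, and minimum, maximum and abnormality outputs use the 30-day period.

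**Conclusion.** The point holds as a minor one. Taken as written, SAP 10.2.4 excludes a completer's Visit 6 and substitutes a value nominally 56 days earlier (laboratory tests, ECG, weight/BMI) or 28 days earlier (vital signs, oral mucosa, C-SSRS). It also disagrees with the safety on-treatment period that SAP 12.8 adopts.

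The reach is limited to descriptive rows labelled last on-treatment and the eGFR category shift to that value. The companion eGFR shift to the lowest value still uses Visit 6. The addendum narrows the reach further: it presents the normal-range shift tables by visit and drops figures. It does not list the eGFR category shift among its exclusions, and it keeps the summaries for laboratory tests, vital signs, weight, ECG and C-SSRS.

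The documents do not support reading this as a deliberate exclusion of end-of-treatment data, nor as a threat to efficacy inference. No hypothesis test uses these rows.

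The conclusion rests on two assumptions: that the comparison is coded strictly, and that the End of treatment form carries no date later than Visit 6. The number of completers affected cannot be given, because enrolment stopped before the planned 446 patients.

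**What to change.** In SAP 10.2.4 or the addendum:
- Define last on-treatment as the last scheduled assessment after IMP Start Date and on or before IMP End Date.
- State that, for patients who completed the treatment phase, nominal Visit 6 also qualifies when it lies within the 10.2.2 safety on-treatment period, and that Visit 7 never qualifies.
- Keep the existing rule that later assessments of early discontinuers who remain on study go to Follow-up, so that no value is classed twice.
- Change the reference in SAP 12.8.3 from Section 10.24 to 10.2.4.

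The cost is a few lines of wording, one changed date condition using the treatment-completion status already summarized under SAP 12.1, and one cross-reference. No new data are needed. The downside is that a completer's Visit 6 held some days after the last dose would be labelled on-treatment.

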10.3 Rescreened Patients Data Handling

A rescreened patient is defined as a patient who fails initial screening attempt because of eligibility criteria violation, is then screen failed and rescreened under a new patient identifier. Rescreened patients will be presented in outputs conducted on the Screening analysis set as two different patients.

10.4 Baseline

10.4.1 Diary Efficacy Based Endpoint

For the primary endpoint of spasm count and the exploratory endpoint of NRS spasm severity score, the baseline is defined as the average of all data collected during the baseline period (as defined in Section 10.2.2) immediately prior to the reference day (as defined in Section 10.2.1).

For the exploratory endpoint of NRS spasticity score, baseline is defined as the average of the last 7 days of electronic diary entries immediately prior to the reference day (as defined in Section 10.2.1) ie from Study Day -1 to -7.

The baseline for the follow-up analysis for spasm count and NRS spasm severity is defined as the average of all data collected during the baseline follow-up period (as defined in Section 10.2.2).

The baseline for the follow-up analysis for NRS spasticity score is defined as the average of all data collected during the period of time starting 6 days before IMP End Date and ending on IMP End Date, ie covers a 7 day period ending on IMP End Date.

10.4.2 Clinic Based Endpoint

For visit based endpoints, the baseline is defined as the last assessment prior to IMP Start Date or prior to randomization if IMP Start Date is after the date of randomization.

However, for C-SSRS, only the assessment carried out at Visit 2 should be used as the baseline assessment.

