# 9.1.2 Visit 2 (Day 1, Randomization)

Following the 28-day baseline period, patients will attend the site for Visit 2 on Day 29, a visit window of +2 days is permitted but it is preferred that the visit is performed on the scheduled visit day, where possible. If, for any reason, the patient is unable to attend the site for randomization within the visit window, the site should contact the Medical Monitor or the sponsor to discuss; please note the eligibility criteria the patient needs to meet should this occur.

The following assessments/procedures will be performed:

- Eligibility check
- Randomization (Section 7.2)
- Concomitant medications review
- AE review
- Physical and oral mucosa examinations
- Body weight measurement
- Vital signs measurement

- 12-lead ECG
- Clinical laboratory blood sampling (hematology and biochemistry)
- Urine drug screen (including THC)
- Urine pregnancy test (if appropriate)
- PK blood sampling (Section 9.2.12.1)
- MSSS-88 assessment (Section 9.2.15.2)
- C-SSRS assessment
- T25FW test (Section 9.2.15.4)
- SF-36 assessment (Section 9.2.15.6)
- IMP dosing training and dispensing (Section 9.2.14.4)

Following predose assessments and after IMP dosing training and IMP dispensing, site staff will provide patients with an example titration schedule and instructions to record IMP dosing information in the patient electronic diary. Patients will take the first dose of IMP on the evening of Visit 2 (Day 1).

See Section 8.1.1 and Section 8.1.2 for IMP dosing and administration information.

Patients should be reminded to record their spasm count, 11-point NRS spasm severity score, 11-point NRS spasticity score, and use of antispasticity medications in the electronic diary once daily, around the same time of the day, preferably in the evening before retiring to sleep. In addition, on the day before Visits 3, 4, and 5 patients will be prompted to record whether they started their morning and evening doses of IMP within 30 minutes of a meal.

Each site will have the option to follow up with the patient through telephone calls during the titration phase to monitor the patient's titration, safety and tolerance, and electronic daily diary reporting.

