# 9.2.10 Vital Signs

As part of the screening procedures at Visit 1, vital signs (systolic and diastolic blood pressure and pulse rate) will first be measured after the patient assumed a supine position for 5 minutes. Where postural blood pressure is required at Visit 1 it should be measured within 2 minutes of assuming a standing position in ambulatory patients only. At all subsequent time points, vital sign measurements will be completed in a sitting position at rest for 5 minutes. Blood pressure must be recorded using the same arm throughout the trial, where possible.

Additional vital signs measurements may be taken during the trial if clinically indicated.

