#### 13.4 General Considerations

Unless stated otherwise, continuous variables will be summarized showing the number of non-missing values (n), mean, standard deviation, median, minimum, and maximum. Categorical variables will be summarized showing the number and percentage of patients falling in each category.

For the primary endpoint of spasm count and the exploratory endpoint of 11-point NRS spasm severity score, baseline is defined as the average of all data collected between Visit 1 and the day before Visit 2.

For the exploratory endpoint of 11-point NRS spasticity score, baseline is defined as the average of the last 7 days of electronic diary entries prior to randomization.

For clinic-based endpoints, baseline is defined as the last record or measure collected prior to the first dose of IMP.

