12.2.3 Baseline Vital Signs

The following baseline vital signs (collected at Screening) including with postural drop assessment will be summarized.

- Screening Supine Systolic blood pressure (SBP) (mmHg),
- Screening Orthostatic SBP (mmHg)
 - Orthostatic SBP being defined as supine SBP- Standing SBP,
- Screening Orthostatic SBP ≤ 20 mm Hg
- Screening Supine Diastolic blood pressure (DBP) (mmHg),
- Screening Orthostatic DBP (mmHg),

Orthostatic DBP being defined as supine DBP- Standing DBP,

- Screening Orthostatic DBP ≤ 10 mm Hg
- Screening Supine Heart Rate (HR) (Beats/min),
- Screening Orthostatic HR (Beats/min)

Orthostatic HR being defined as supine HR- Standing HR,

• Proportion of patients who meet criteria for orthostatic hypotension defined as either drop in SBP of 20 mmHg or greater or drop in DBP of 10 mmHg or greater.

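### SAP 10.4.2 ties the clinic baseline to the dispensing date, so a program that follows it literally would drop the predose Visit 2 values and run the safety analyses from screening

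*SAP*

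**What the plan says.** The protocol rule (13.4) for clinic-based endpoints is that "baseline is defined as the last record or measure collected prior to the first dose of IMP". Protocol 9.1.2 puts that first dose on the evening of Visit 2, after the predose assessments.

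The SAP rule (10.4.2) replaces the dose with a date: "the baseline is defined as the last assessment prior to IMP Start Date or prior to randomization". The randomization limb is conditional on the IMP Start Date falling after randomization. C-SSRS is then singled out to take Visit 2 as its baseline. The date itself comes from SAP 10.1: "The IMP Start Date will be assumed to be the first date of IMP dispense, which will be obtained from the IRT data". Protocol 5.3.4 fixes when dispensing begins: "IMP will be dispensed at Visits 2, 3, 4, and 5".

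Other SAP text points to Visit 2 predose as baseline:
- 10.2.2 ends the baseline period for clinic endpoints on Day 1, before the first intake.
- Table 10.2-1 gives MSSS-88, T25FW and SF-36 a baseline window that runs up to Day 1 predose.
- 10.18 (MSSS-88) and 10.21 (T25FW) label the Day 1 visit as baseline.
- 6.2 declares no change from the protocol.

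On posture, Protocol 9.2.10 measures vital signs supine at Visit 1, and then: "At all subsequent time points, vital sign measurements will be completed in a sitting position at rest for 5 minutes". SAP 12.2.3 nevertheless introduces the screening table as baseline: "The following baseline vital signs (collected at Screening) including with postural drop assessment will be summarized".

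**The concern.** The substitution looks harmless, but on schedule the dispensing date and the Visit 2 date are the same day. An assessment made on a date is not prior to that date. The rule that SAP 12.2 points to for baseline definitions therefore excludes the values that the protocol intends as baseline.

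The stakes differ by endpoint. MSSS-88 is the only secondary endpoint that is formally tested, and the addendum keeps its inferential analysis. Its baseline should not depend on which of two conflicting SAP sections a programmer follows. For safety data the risk is quieter. An earlier value exists at Visit 1, so a program that follows 10.4.2 literally would produce complete tables with the wrong reference value and no warning.

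**Working it through.** The plan gives no figure to reproduce here. The check applies two candidate rules to the schedule of assessments.

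**Dates.** By SAP 10.2.1, study day on or after the reference date is assessment date − reference date + 1, and before it is assessment date − reference date.
- Visit 2, on the randomization date: 0 + 1 = Day 1.
- Visit 1, 28 days earlier with a +2 day window on Visit 2: Day −28 to Day −30.
- IMP Start Date = first dispense = Visit 2 = Day 1.

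**Rules.** (a) Literal 10.4.2: assessment date < IMP Start Date, so Day −1 or earlier. (b) Predose rule of Protocol 13.4 and SAP 10.2.2: last assessment before first intake, so Visit 2 is included.

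| Endpoint | Collected before first dose (Protocol Appendix 1) | Baseline under (a) | Baseline under (b) |
|---|---|---|---|
| MSSS-88, SF-36, T25FW | Visit 2 | none | Visit 2 |
| Laboratory tests, ECG, weight, oral mucosa | Visits 1 and 2 | Visit 1 | Visit 2 |
| Vital signs | Visits 1 and 2 | Visit 1, supine | Visit 2, sitting |
| C-SSRS | Visits 1 and 2 | Visit 2 (named) | Visit 2 |

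**Does the randomization limb help?** It is reached only if the IMP Start Date is after randomization. On schedule both fall on Day 1, so it is not reached.

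**Is (a) a natural way to code the sentence?** Yes. SAP 10.2.1 separates assessments on or after a date from those prior to it. SAP 12.8.1 classifies adverse events before, against on or after, the IMP Start Date in the same way. SAP 10.4.1 refers to the 10.2.2 baseline period for diary endpoints; 10.4.2 does not.

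**Effect on vital signs.** Under (a) the recorded change splits into two parts:

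later sitting − Visit 1 supine = (later sitting − Visit 2 sitting) + (Visit 2 sitting − Visit 1 supine)

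The first bracket is the change the protocol intends. The second is posture plus four weeks of pre-treatment drift, and it enters every later visit for that patient. Table 12.8-2 needs both an absolute value and a change (for example SBP below 90 mmHg and a fall of at least 20 mmHg). Only the change criterion moves, so the counts can shift only among patients who meet the absolute criterion. The documents give no supine-to-sitting difference, so the shift cannot be put in mmHg.

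**What the addendum keeps.** It retains laboratory tests, vital signs, ECG, weight (12.8.5.1) and oral mucosa (12.8.5.6). T25FW and SF-36 become listings only, and 12.2.3 is not among the listed sections.

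**The case against.** The strongest reply is that the intended reading is clear and a competent programmer would find it. Much of this stands. Table 10.2-1 and 10.18 fix the MSSS-88 baseline at Day 1 predose, and 10.2.2 covers all clinic endpoints. For safety data, SAP 12.8.4 analyses sitting values and lists changes from Visit 3 onwards, so Visit 2 has no role except as baseline. SAP 12.8.3 collects laboratory samples at Screening and Visits 2, 4 and 6 but reports Baseline, Visit 4 and Visit 6. Protocol 13.6.5.4 names screening and baseline separately. In SAP 12.2.3 the blood pressure and heart rate rows are each labelled as screening values, so that table does not set the reference for change.

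A reader might infer three stronger things that the documents do not support:
- *That MSSS-88 has no baseline.* This follows only if 10.4.2 is applied alone and the endpoint-specific text is ignored. A baseline missing for every patient would also be noticed at once.
- *That the Visit 2 assessments follow randomization because Protocol 9.1.2 lists them after it.* That list is not chronological. It also puts the urine pregnancy test after randomization, while the Appendix 1 footnote requires that test before it.
- *That only C-SSRS has a stated Visit 2 baseline.* Table 10.2-1, 10.18 and 10.21 name it for other endpoints.

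What the reply does not remove is that 10.4.2 is the explicit SAP baseline rule and gives a different answer. For safety data no window table overrides it: SAP 10.2.4 uses nominal visits but does not define baseline. SAP 12.8.4 also lists Screening among the vital-signs timepoints and bars only standing measurements from the abnormality criteria.

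**Conclusion.** The inconsistency is real and should be corrected. Read as a date comparison, 10.4.2 contradicts Protocol 13.4, SAP 10.2.2, Table 10.2-1 and 10.18, and the difference is not declared in 6.2.

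For MSSS-88 the consequence is a conflict between sections with a clear intended answer. For the retained safety analyses it is a silent error if the rule is coded literally. For every patient on schedule, the reference value would come from Visit 1, 28 to 30 days before Visit 2, and for vital signs it would be supine. Randomization should balance the posture shift between arms, so the distortion falls mainly on within-arm changes and abnormality counts.

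This rests on three assumptions: dispensing happens on the day of Visit 2, the comparison is made on dates and not clock times, and the programmer follows 10.4.2 ahead of 10.2.2. The wording conflict is certain; whether it reaches the output is not.

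**What to change.** Reword SAP 10.4.2 along these lines: *baseline is the last non-missing assessment before first IMP intake; scheduled Visit 2 assessments are predose and are included.* Keep the C-SSRS sentence.

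Add to SAP 12.8.4: *change from baseline in vital signs uses the sitting Visit 2 value.*

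Relabelling the 12.2.3 table as screening values would remove a source of confusion, but it is optional because the addendum does not list that table.

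The cost is two sentences in the SAP or its addendum before unblinding, and a check that the baseline flags in the analysis datasets fall on Visit 2. No new data are needed and no planned figure changes.
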